### **B. Study Objectives**

**Aim 1:** Test the neurobehavioral adaptions in response to repeated intake of branded SSBs relative to unsweetened, flavored control beverages (USB).

*We hypothesize that daily SSB intake will lead to:*

- a. *increases in parietal/occipital brain response during exposure to the SSB brand;*
- b. *decreased dorsal prefrontal and hippocampal response to the SSB brand;*
- c. *reduced striatal response during receipt of the assigned SSB,*

*relative to baseline and to those who are assigned to consumed the control beverage.*

**Aim 2:** Test whether BMI mediates the neurobehavioral response patterns to the consumed beverages as a function of daily SSB intake relative to baseline and to those who are assigned to consume USB.

*We hypothesize that there will be no significant interaction, such that those individuals with elevated BMI will show no difference than those at a lower BMI in the brain adaptions described in Aim 1.*

**Aim 3:** Test the impact of repeated consumption of SSBs on behavioral responses (reaction time and response inhibition) to the beverage brands measured by the stop sign task (SST).

*We hypothesize that mean reaction time to Go trials will result in a significant interaction of group assignment (sugar vs. control) by pre-/post- daily consumption. Specifically, we hypothesize that the sugar group will show a decreased reaction time to Go trials, representing faster responses relative to the control group and baseline.*

**Aim 4:** Test the impact of repeated consumption of sugar-sweetened beverage on perceptual hedonic and taste ratings.

*We hypothesize that daily beverage intake will lead to:*

- a. *no change in pleasantness and desire ratings as a function of repeated consumption of the assigned beverages.*
- b. *an assignment (sugar vs. control) by time (pre-/post- daily consumption) interaction for desire ratings of the non-assigned beverages. Specifically, we hypothesize that there will be a decrease in desire ratings of the control beverage after having consumed a SSB daily. We expect no change in pleasantness.*

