### D. Study Duration, Enrollment and Number of Subjects

For each participant, the study will include 2 pre-intervention visits, 2 post-intervention visits, and 9 in-lab assessments during the 21-day intervention period. Total study duration will be approximately two years. We will recruit 230, 18-28-year-old healthy individuals. Stratified randomization techniques will be used to distribute: 1) male & females, 2) those with a BMI > 26.1 & those with a BMI < 26.1 equally across the 2 experimental conditions (SSB vs. unsweetened beverage) and then to the two flavors within each experimental condition. BMI of 26.0 was selected as it is the midpoint of inclusion criteria 18 < BMI < 34. Experimental and flavor conditions will be blinded to those performing analyses.

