## **Statistical Analysis Cover Page**

**Official Title: Neurobehavioral Plasticity to Regular Sugar-Sweetened Beverage Intake: An fMRI Experiment**

**NCT Number: NCT03490734**

**Document Date: January 25, 2023**

## **Statistical Analysis Plan**

### **A. Sample Size and Power**

Data collection was ended early due to COVID-19 (ending March 2020), resulting in a lower than anticipated sample size (160 vs. 230), which may impact results, specifically, measures of individual differences. As our sample was smaller than anticipated we performed a sensitivity analysis using Gpower (ver. 3.1.9.7, Heinrich Heine University Düsseldorf) for the primary hypothesis using alpha = 0.05, power of 0.80 and a total sample of 123 (accounting for missing data, incomplete data collection, etc.), and we are still able to detect effect of 0.25. Inclusion Criteria: Potential participants were eligible for the study if they had BMI scores between 18 and 34 at baseline. Exclusion Criteria: Individuals with probable current Axis I psychopathology or any fMRI contra-indicators (e.g., metal implants, braces) were excluded. Those with a probable Axis I diagnosis will be provided with treatment referral information and encouraged to seek treatment, current regular use (3 or more times a week) of psychoactive drugs (e.g., cocaine, marijuana, nicotine), regular smoking, serious medical problems (e.g., cancer, diabetes), dietary practices that do not allow for intake of intervention beverages.

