**fMRI primary analyses:** Neuroimaging analyses were primarily completed in FSL (FMRIB Software Library, [www.fmrib.ox.ac.uk/fsl](http://www.fmrib.ox.ac.uk/fsl)). Individual (level 1), within-subject (level 2), and group level (level 3) analyses were carried out in FSL's fMRI Expert Analysis Tool (FEAT). At the 1st (individual) level, SSB, USB, SSB logo, USB logo vs. water logo contrasts were created. These were carried forward to a within-subject (level 2) model testing for the effect of time.

At the 2nd (within-subject) level analyses, the above SSB, USB, SSB logo, USB logo vs. water logo data were put into a within-subject t-test testing individual-level differences as a function of time, i.e., post-intervention > pre-intervention (testing for increases in BOLD response as a function of the intervention) and pre-intervention > post-intervention (testing for decreases in BOLD response as a function of the intervention).

Level 3 (group-level) analysis used the resulting level 2 data (post- > pre-intervention; SSB/USB > water taste/logo to test for increases in response and, separately, pre- > post-intervention; SSB/USB > water taste/logo for decreases in response) to test for the main effect of the intervention and the interaction of BMI (**Aims 1 and 2**).

- a. First, the assignment\*BMI interaction (**Aim 2**) is tested with flavor assignment, gender, thirst, and beverage pleasantness as covariates of no interest. By using the level 2 within-subject data that tested for the effect of time, this results in a time\*group\*BMI interaction. Contrasts of interest for the group model are SSB > water and SSB logo > water logo. This is tested with the pre- > post-intervention and the post- > pre-intervention level 2 data. Parameter estimates of significant BOLD response are plotted for visualization purposes.
- b. **Aim 1** is tested in a separate model controlling for BMI (no interaction), flavor assignment, gender, thirst, and beverage pleasantness. Contrasts of interest for the group model are SSB > water and SSB logo > water logo. This is tested with the pre- > post-intervention and the post- > pre-intervention level 2 data. Mean

cluster parameter estimates of significant BOLD response are plotted for visualization purposes.

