All group-level analyses were corrected for multiple comparisons by using the threshold free cluster enhancement (TFCE), nonparametric thresholding algorithm in FSL's RANDOMISE (n permutations = 10000), resulting in a family-wise error rate corrected significance threshold of  $p_{FWE} < 0.05$ . At the group level, functional data were masked via an inclusive grey matter mask to reduce the number multiple comparisons, resulting in whole brain, grey matter analyses. The mask was created via the ICBM 2009c Nonlinear Asymmetric template that was binarized at a threshold of 0.04 using FSLmaths. Localization of significant clusters will be used and determined using Mango's MNI atlas tool.

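### Aim 1 compares arms on pre/post BOLD change without the pre-intervention map as a covariate, which is unbiased but gives up precision at each voxel unless the post-on-pre slope is 1

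*SAP*

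**What the plan says.** The SAP's fMRI primary analyses (section B.1) work in three levels. At level 2 the first-level contrasts "were put into a within-subject t-test testing individual-level differences as a function of time", which gives one pre/post difference map per participant and contrast. Level 3 takes those maps as the outcome. Item b tests Aim 1 by comparing arms on SSB > water and SSB logo > water logo, "controlling for BMI (no interaction), flavor assignment, gender, thirst, and beverage pleasantness". Neither the preprocessing, level 1 to 3 nor correction text names a pre-intervention BOLD map, or a regional baseline value, as a regressor. Inference is whole-brain within a grey matter mask, using TFCE with 10000 permutations and family-wise correction.

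The comparison follows the Protocol's Aim 1 hypotheses (section B), which are framed "relative to baseline and to those who are assigned to consumed the control beverage". Under Protocol section G (fMRI scan paradigms), the task covers receipt of both drinks, and everyone sees the SSB and USB logos of the assigned flavor whichever arm they are in. The pre-intervention SSB maps therefore mean the same thing in both arms.

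SAP section A reports that collection stopped at 160 of 230 participants. It bases its sensitivity analysis on 123, at alpha 0.05 and power 0.80, and concludes that "we are still able to detect effect of 0.25".

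**The concern.** A change score fixes the weight on the baseline at exactly 1. If the regression slope of post on pre differs from 1, part of the baseline variation stays in the change score as noise.

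The same thing can be seen through chance imbalance. With 62 and 61 per arm, the standard error of the arm difference in a baseline value is √(1/62 + 1/61) = 0.18 baseline SD. An unadjusted change score carries (slope − 1) times whatever imbalance occurs into the estimate. This averages to zero over randomizations, so it is extra variance and not bias. Including the baseline as a covariate removes it.

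The sample fell well short of plan, and the maps needed for the adjustment already exist for everyone in the change analysis. The precision of the Aim 1 arm comparison is what is at stake.

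**Working it through.** **1. The plan's own figure.** Inputs from SAP section A: N = 123, alpha 0.05, power 0.80. Two-sided testing and an even arm split are assumed, since neither is stated. A two-group F test with noncentrality f²N has a minimum detectable f of 0.255, and power at exactly f = 0.25 is 0.785. A correlation fits as well: tanh[(1.960 + 0.842)/√120] = 0.250. The stated 0.25 is therefore reproducible, but under two different effect measures, and the SAP names neither.

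**2. Variance of the arm difference.** Let ρ be the pre/post correlation of the contrast at a voxel and k the ratio of post SD to pre SD. The slope of post on pre is then ρk. In units of the pre variance, the residual variance per participant is:

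- change score: 1 + k² − 2ρk
- change score with the pre-intervention value as covariate: k²(1 − ρ²)

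The first minus the second is (1 − ρk)². This is never negative, and it is zero only when the slope is 1. The ratio, adjusted over planned, is k²(1 − ρ²)/(1 + k² − 2ρk). With k = 1 it reduces to (1 + ρ)/2.

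**3. Numbers.** The documents give neither ρ nor k, so both are assumed over a range:

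| ρ | k = 0.8 | k = 1 | k = 1.25 |
|---|---|---|---|
| 0.3 | 0.502 | 0.65 | 0.784 |
| 0.5 | 0.571 | 0.75 | 0.893 |
| 0.7 | 0.628 | 0.85 | 0.981 |
| 0.8 | 0.640 | 0.90 | 1.000 |
| 0.9 | 0.608 | 0.95 | 0.950 |

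Example: k = 1.25 and ρ = 0.8 give 1.5625 × 0.36 = 0.5625 over 1 + 1.5625 − 2 = 0.5625, a ratio of 1. The slope there is 0.8 × 1.25 = 1. For k = 1 the standard error is the square root of the ratio: 0.806, 0.866, 0.922 and 0.975 of its planned value at ρ = 0.3, 0.5, 0.7 and 0.9.

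**4. Check at the trial's size.** In 20,000 simulated trials per ρ (62/61, five further covariates in both models, k = 1, no true effect), the variance ratios were 0.663, 0.750, 0.847 and 0.958 at ρ = 0.3, 0.5, 0.7 and 0.9. Type I error was 0.048 to 0.052 in both models, and bias was at most 0.002. In a further 6,000 trials per ρ with a true effect of 0.30 (ρ = 0.3, 0.5, 0.7), the change model averaged 0.301 to 0.303 and the adjusted model 0.300 to 0.304.

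**5. Cost in degrees of freedom.** The planned model has an intercept, an arm term and five covariates, which leaves 123 − 7 = 116 error degrees of freedom. The adjusted model leaves 115.

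**The case against.** The strongest reply is that nothing here is wrong. The change-score comparison is a group-by-time test, as in the SAP's models for Aims 3 and 4 and the exploratory questionnaires, and it matches the wording of the Aim 1 hypotheses. The gain depends on two quantities the documents do not give and disappears in part of the plausible range. If imaging results are known, an adjusted analysis can no longer sharpen the primary inference.

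All of this stands. It limits the point to precision and decides how the fix must be labeled. It does not remove the point: adjustment leaves the arm contrast and its baseline reading intact, and its worst case is about 1 degree of freedom.

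Three stronger readings are tempting, and the documents do not support them:

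- **The 0.25 could be rescaled.** A reader might multiply by the standard-error factors and claim a detectable effect of 0.25 × √0.65 = 0.20 to 0.25 × √0.95 = 0.24. The effect measure is not named and 0.25 fits more than one, so the conversion is conjecture.
- **The 123 would act like a larger trial.** At ρ = 0.5 and k = 1, 123/0.75 = 164. That equivalence describes variance at a single voxel. Aim 1 is decided by TFCE with family-wise correction, and its power cannot be computed from the documents.
- **Analyst blinding makes a switch of primary model safe.** Protocol section D says "Experimental and flavor conditions will be blinded to those performing analyses". That hides the labels, but a blinded analyst may already have seen a map comparing the two unlabeled arms.

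**Conclusion.** The point holds as a matter of efficiency. With equal pre and post SDs, item b's arm difference has a variance that adjustment would cut by 35%, 25%, 15% and 5% at ρ = 0.3, 0.5, 0.7 and 0.9. The gain is larger if post SD is below pre SD. It is smaller over most of the range, and nil at ρ = 0.8, if post SD is 1.25 times pre SD. It will differ by voxel and contrast.

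The figures assume a linear slope common to both arms and further covariates unrelated to the BOLD contrast. Otherwise ρ and k should be read as values after allowing for those covariates.

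A reader might infer that Aim 1 is biased or invalid because baseline is left out. It is not: under randomization the omission causes no bias, and both models held their error rate in simulation. That statement covers the baseline omission only. Nor do the documents show the sample to be inadequate. This is an inexpensive improvement worth making, not the repair of an error.

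**What to change.** Keep the change map as outcome and add each participant's own pre-intervention contrast map as a voxelwise covariate: SSB > water for receipt, SSB logo > water logo for the logo. Leave the mask, TFCE and permutation settings as they are.

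The status of the result depends on what has been seen. The SAP is dated January 2023, collection ended in March 2020, and the FEAT analyses and the group-level correction are described in the past tense, while item b is in the present tense. The sponsor should therefore state which case applies:

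- **Any group-level arm comparison map has been viewed, with or without condition labels.** Item b stays primary. Suggested text: *Added after group-level imaging maps had been viewed: the Aim 1 model is refitted with the participant's pre-intervention contrast map as a voxelwise covariate. Both results are reported side by side.*
- **No such map has been viewed.** The adjusted model may be named primary, with the date of that decision recorded.

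The cost is SAP wording, about 1 degree of freedom, and a rerun of the level 3 permutation models, which will take longer with a voxelwise covariate. No new data are needed. If results are already known, the adjusted model supports the primary result and does not replace it.

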### C. Study Design

We propose to use a randomized control trial design and recruit 230 18-28 year old men and women over a 42-month period to address the proposed aims. Participants will be randomly assigned to an experimental condition (sugar-sweetened beverage [SSB] or unsweetened, flavored control [USB]) and then to one of two flavors within their experimental condition. This results in 4 cells: two flavors high-sugar beverages (n=115; 58/57 for each flavor of SSB) and the same two flavors of unsweetened control beverages (n=115; 58/57 for each flavor of control). The two-tiered randomization process allows for a fully powered test of the effects of SSB consumption (n=115) versus unsweetened control (n=115; Aim 1) and individual difference factors (Aims 2-4). Participants will complete the pre-intervention assessments (see **Table 1 & Study Procedures**), then begin the intervention which will include the daily consumption of their flavored beverage for 21 days. Following the intervention, participants will come back in the lab to complete the post-intervention assessments (see **Study Procedures**).

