Explicit hedonic, taste and internal state ratings assessed via visual analog scales (VAS). Explicit hedonic scales were used to evaluate characteristics of the beverages, including pleasantness, desire, sweetness, bitterness, intensity, and familiarity insight into alterations the perceptual hedonic value of the beverages. Measures of internal state: hunger, fullness, thirst, and nausea were also collected. For perceptual hedonic assessments, labeled hedonic scales and generalized labeled magnitude scales provide a ratio-like data with the ability to compare individual differences in a more sensitive way than traditional scales. The participant consumed a small amount of the beverage and completed the associated scale (e.g., pleasantness). Additionally, similar internal state scales were assessed via 200mm cross-modal visual analog scales at all assessments. Scales of all beverages (SSB, USB; both flavors) were collected on the pre- and post-intervention behavioral visits. Scales for assigned beverages only were also collected on the pre- and post-intervention scan visits.

Stop signal task (SST). The Stop-Signal Task measures motor response time, accuracy, and response inhibition. The task was performed on an iPad app where participants underwent 6 total runs at the pre-intervention behavioral visit and at the post-intervention behavioral visit. Three of these runs were of their assigned condition, where the logo of their assigned beverage

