For **Aim 4**, perceptual hedonic, taste and internal state ratings (assessed using visual analog scales (VAS)) are analyzed. Data from pre- and post-intervention perceptual ratings are

analyzed using PROC MIXED implemented in SAS (Version 9.4, Cary, NC). Pleasantness and Desire of the assigned beverage (pre-/post-intervention) are each entered into 2x2 repeated measure mixed models, including group-by-time interactions. Control variables of no interest to be included are BMI, assigned flavor, gender, and thirst. Four pairwise comparisons of interest (pre- and post-intervention differences by intervention assignment and within-assignment change over time) are probed. Tukey-adjusted two-tailed  $p$ -values less than 0.05 are considered significant.

**fMRI data preprocessing:** Neuroimaging data were preprocessed using the fMRIPrep pipeline. DICOMS were converted to the Brain Imaging Data Structure (BIDS file structure), then preprocessed using fMRIPrep. Prior to preprocessing, the first four volumes of each functional run were trimmed. fMRIPrep preprocessing included skull stripping using Advanced Normalization Tools (ANTs); tissue segmentation using FSL's Automated Segmentation Tool (FAST); and spatial normalization to Montreal Neurological Institute (MNI) 152-Asymmetrical space using ANTs' registration option. Functional data were co-registered to anatomical data using FSL's FMRIB's Linear Image Registration Tool (FLIRT) with boundary-based registration. Functional data were additionally motion corrected using FSL's MCFLIRT and corrected for fieldmap distortion. In FSL, final preprocessing included spatial smoothing using a 5mm full width half maximum isotropic Gaussian kernel, high-pass filtering, adding temporal derivatives, adjusting for autocorrelation, and adjusting for nuisance regressors, including the 6 motion parameters, 6 anatomical component-based noise correction regressors (aCompCor), and high motion time points (FD>0.5mm). A functional run for a subject was excluded if >30% of total volumes were flagged as high motion points.

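### The fMRI group models adjust for beverage pleasantness without defining it, and the scan-visit rating is of a different drink in each arm

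*SAP*

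**What the plan says.** SAP section B.1 (fMRI primary analyses) analyses one post-versus-pre change image per participant at Level 3. Model (b), for Aim 1, is run "controlling for BMI (no interaction), flavor assignment, gender, thirst, and beverage pleasantness". Model (a), for the assignment-by-BMI interaction of Aim 2, has "flavor assignment, gender, thirst, and beverage pleasantness as covariates of no interest". For both, "Contrasts of interest for the group model are SSB > water and SSB logo > water logo", so the imaging outcome concerns the sweetened drink whichever arm the participant is in. Neither model names the drink, visit or time point of the pleasantness value, and no model without it is planned.

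Protocol section G says that all beverages, sweetened and unsweetened in both flavors, were rated at the behavioral visits before and after the intervention. For the scan visits it says: "Scales for assigned beverages only were also collected on the pre- and post-intervention scan visits".

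For Aim 4 the SAP treats the same kind of rating as an outcome: "Pleasantness and Desire of the assigned beverage (pre-/post-intervention) are each entered into 2x2 repeated measure mixed models", with a group-by-time interaction. Thirst appears in the Aim 4 models only as a control variable.

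**The concern.** A covariate in a randomized comparison is safe when it is measured before the intervention and means the same thing in both arms. Several readings of this covariate fail that test.

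- **Assigned-drink rating at a scan visit.** The value depends on which drink the participant was assigned. Even the pre-intervention value can differ between arms, because one arm rates a sweetened drink and the other an unsweetened one. Holding it equal compares SSB participants with controls who like the unsweetened drink as much, which is not the randomized comparison. For controls it is also not a rating of the drink in the tested contrast.
- **Post-intervention or change value.** This conditions on something the intervention may alter, and Aim 4 is set up to find out whether it does.

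At stake is the meaning of the primary imaging result. The adjusted coefficient would no longer be the total effect of assignment, and it could be too small or too large. The permutation-based correction does not repair this, because it controls error for the adjusted effect.

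**Working it through.** **1. The plan's own figure.** SAP section A gives "alpha = 0.05, power of 0.80 and a total sample of 123" and states that "we are still able to detect effect of 0.25", without naming the metric. For a two-group F test (noncentral F, N = 123, alpha 0.05, power 0.80) the detectable Cohen's f is 0.2546, and power at f = 0.25 is 0.785. The figure therefore reproduces as f between two groups. With equal arms d = 2f, so f = 0.25 is d = 0.50, which I use as the true arm effect. A paired standardized difference of about 0.253 would also fit. A two-time repeated-measures group-by-time f would not (0.127 at a pre/post correlation of 0.5). The 0.25 is not in dispute here.

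**2. Inputs.** N = 123 is from the SAP, and 1:1 allocation is from Protocol section C. Two quantities are assumptions, because the documents give neither:
- g = arm gap in the pleasantness covariate, in within-arm SDs
- r = within-arm slope of BOLD change on pleasantness, in SDs per SD

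**3. Formulas.** For a covariate entered raw:
- adjusted arm effect = total effect - r × g
- SE = √[(4/N) × (1 + g²/4) × (1 - r²)]

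The shift is zero if either g or r is zero.

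**4. Worked case: g = 0.5, r = +0.3.**
- Adjusted effect = 0.50 - 0.3 × 0.5 = 0.35
- SE = √[(4/123) × 1.0625 × 0.91] = 0.177
- 0.35/0.177 = 1.97, against a critical value of about 1.98, so power is about 0.50
- With no total effect the coefficient centres on -0.15; 0.15/0.177 = 0.85, so rejection is about 13% instead of 5%

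**5. Range.**

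| g | r | Adjusted effect (true 0.50) | Power | Rejection when total effect is zero |
|---|---|---|---|---|
| 0 | 0 | 0.50 | 0.79 | 5% |
| 0 | ±0.3 | 0.50 | 0.82 | 5% |
| 0.5 | 0 | 0.50 | 0.76 | 5% |
| 0.5 | +0.3 | 0.35 | 0.50 | 13% |
| 0.5 | -0.3 | 0.65 | 0.95 | 13% |
| 0.8 | 0 | 0.50 | 0.72 | 5% |
| 0.8 | +0.3 | 0.26 | 0.28 | 25% |

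**6. Slope in one arm only.** In controls, liking of the USB need not relate to the response to the SSB. With slope 0.3 in the SSB arm and 0 in controls, the pooled slope is about 0.15. The shift at g = 0.5 is then 0.15 × 0.5 = 0.075, the estimate is about 0.43, and null rejection is about 6 to 7%.

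**7. Check.** A simulation of 20,000 trials per case, N = 123, g = 0.5, gave:
- slope +0.3 in both arms: estimate 0.349, null rejection 13.5%
- slope -0.3 in both arms: estimate 0.650, null rejection 13.7%
- slope in the SSB arm only: estimate 0.422, null rejection 7.2%

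All these figures are for a single test of the Aim 1 arm effect. They do not model whole-brain TFCE with family-wise correction, and they do not carry over to the Aim 2 interaction.

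**The case against.** The strongest reply is that the SAP never says the covariate is the scan-visit rating. Everyone rated all drinks at the pre-intervention behavioral visit, so a sound covariate fits the wording. This stands: a reader might infer that the primary model is biased as run, and the documents do not show that.

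The scan-visit limit also rests on one sentence. Protocol Table 1 marks the assigned-drink restriction for the intervention period only, and the scan-visit outlines in section F list the taste test without it. Section G is the explicit statement and the better reading, but the passages are not fully aligned.

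A reader might go further and infer that every use of a scan-visit rating is unsound. That does not follow. Centering the rating within arm removes the gap, and a change score cancels a constant level difference between the drinks. If pleasantness then changes equally in both arms, as the Aim 4 hypothesis of no change would imply, nothing is shifted. But that hypothesis is under test, and the SAP states no centering.

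On size, nothing in the documents supports a particular gap. The pilot in section G (n = 27) reports similar palatability across flavors and similar willingness to drink both versions. It does not state a comparison of liking between SSB and USB, so it neither establishes a gap nor rules one out.

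The argument does not extend to thirst, although thirst sits beside pleasantness in both models. Thirst is not drink-specific and is not a modelled Aim 4 outcome. Only a post-intervention value would raise a question, and a weaker one.

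**Conclusion.** The concern holds in a limited form. Both Level 3 models contain a pleasantness covariate that the SAP leaves undefined. The value collected alongside the scan is, by Protocol section G, of a different drink in each arm, and its post-intervention or change versions involve a variable that Aim 4 tests as an outcome. This is more than a missing detail, because the choice left open can move the primary arm effect.

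Neither size nor direction can be settled from the documents. A gap of 0.5 SD with a common slope of 0.3 in absolute value moves a 0.50 SD effect by 0.15 either way, and a slope in the SSB arm alone moves it by about half that. If gap or slope is zero there is no bias. A gap with zero slope costs only a little power (0.79 to 0.76 at a gap of 0.5). All of this assumes the covariate is entered raw and that 0.25 in the SAP means Cohen's f.

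**What to change.** In models (a) and (b), define the pleasantness covariate as the pre-intervention rating of the SSB in the participant's assigned flavor, from the behavioral visit. Section G says all beverages were rated there, so the rating refers to the same kind of drink in both arms and precedes the intervention. Keep thirst, specified as the pre-intervention scan-visit value; it is an acute state, and the behavioral visit falls 1-3 days earlier.

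Label any model using assigned-drink, post-intervention or change pleasantness as a sensitivity or exploratory mechanism analysis.

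Data collection ended in March 2020 and the SAP describes much of the imaging analysis in the past tense, so a change of covariate now is itself post hoc. Disclose the definition as a clarification, state which rating was used in the models already run, and report those results beside the redefined ones.

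The cost is a short SAP amendment and a rerun of the Level 3 models with data already collected.
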